10.3.5. Exploratory Analyses

10.3.5.1. Incidence of surgical Escharotomy procedures on circumferential extremities target wounds

For each circumferential extremity target wound a binary (yes/no) variable will be computed, indicating whether this wound was escharotomized. Furthermore, a binary (yes/no) variable for each patient with at least one circumferential extremities target wound will be computed indicating whether this patient had at least one circumferential extremities target wound which was escharotomized.

10.3.5.2. Incidence of reduction in interstitial/compartment pressure in circumferential extremities target wounds

Interstitial/compartment pressure in circumferential extremities target wounds is measured within 1 hour (+15 min) prior to start of each eschar removal procedure and post-eschar removal. For each circumferential target wound and each eschar removal procedure a binary (yes/no) variable will be computed indicating whether reduction in interstitial/compartment pressure in that wound was present during the procedure.

10.3.5.3. % wound area surgically excised for eschar removal

% of wound area surgically excised for eschar removal, A_{total}, will be calculated per patient using the following formula:

$$A_{total} = \frac{\sum_{i} (a_i * \%TBSA_i)}{\sum_{i} \%TBSA_i}$$

where %TBSA_i is the area of TW i (in % TBSA) and a_i denotes the % of wound area surgically excised for eschar removal of TW i. The sums refer to all TWs of a patient.

For TWs that were treated for eschar removal with NexoBrid and/or non-surgical procedures only, the a_i will receive the value of 0.

For TWs that were treated for eschar removal with at least one surgical procedure and no corresponding % area excised is available, the value of a_i will be set to missing. Consequently, for subjects having such TWs, A_{total} will be set to missing.

10.3.5.4. Incidence of surgically harvested donor sites wounds

For each patient, the number of donor site wounds will be calculated.

Not all donor sites are numbered during wound management and re-admissions. Therefore, Donor sites will be identified in SDTM domain PR and duplicates for donor sites already numbered will be deleted. For donor sites not already numbered but only described by the anatomical location, only one entry per procedure date and anatomical location will be kept. The remaining entries are all considered as separate donor sites and numbered under consideration of already numbered donor sites. That means, even if the anatomical location is equal, entries with no donor site number are considered as separate donor sites if the procedure date differs.

10.3.5.5. % area of surgically harvested donor site wounds

For each autograft procedure the % TBSA of the donor site is captured. These values will be summed up over all autograft procedures for each patient giving the % area of surgically harvested donor site wounds.

10.3.5.6. Blood loss using changes in hemoglobin following eschar removal procedures

For each debridement procedure, the change in hemoglobin will be calculated as the difference of the hemoglobin value before the procedure and the hemoglobin value 4 hours post the procedure. This difference in hemoglobin values will be summed for each patient.

Furthermore, for each patient, the difference of the hemoglobin value prior to the first debridement procedure and the hemoglobin value 4 hours post the last debridement procedure will be calculated.

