7.2.4. Exploratory Analyses

- Incidence of surgical Escharotomy procedures on circumferential extremities target wounds.
- Incidence of reduction in interstitial/compartment pressure in circumferential extremity wounds,
- Reduction in surgical needs as measured by an analysis of % wound area surgically excised for eschar removal.
- Reduction in surgical need as measured by analysis of incidence of surgically harvested donor sites scars,
- Reduction in surgical need as measured by analysis of % area of surgically harvested donor site scars.
- Blood loss related to eschar removal assessed by changes in Hemoglobin incurred during the eschar removal procedures
- PK evaluation in NexoBrid patients
- Cosmesis evaluation (MVSS and POSAS) will be used to assess the quality of the donor site scars,
- Incidence of wound closure
- Additional Cosmesis and Function evaluation will be performed using POSAS measured at 12 and 24 months from wound closure.
- Incidence and extent of Autograft in DPT wounds
- Duration of hospitalization

Statistical Analysis Plan V02 of 31 May 2021

⁴ BOQ will be completed only for patient from study sites in the USA. BOQ₁₁₋₁₈ will be completed by patients aged 11-18. BOQ₀₋₅ will be completed by parents of burned children under the age of 5 years and BOQ₅₋₁₈ will be completed by parents of burned children between the ages of 5 and 18

8. Handling of Protocol Violations

Before database lock and statistical analysis, possible protocol violations will be discussed by data management, sponsor, PI and his/her proxy and the statisticians and classified as minor or major violations. The list with all protocol violations will be prepared by the data management.

A protocol violation will be classified as major if

- The treatment differs from the planned treatment (randomization arm), or
- There was drug misuse (this may include application time deviated in 25% or more, deviation of more than 20% in the TBSA area treated in one session at a time, if relevant, error in drug preparation (e.g. 2g mixed in 50g), storage temperature below 2°C 8°C or >24h at room temperature and used without any stability confirmation by sponsor), or
- treatment started more than 5 days from injury, or
- one of the following inclusion criteria is violated:
 - o Stage 1: Males and females between 4 years to 18 years of age,
 - Stage 2 (upon DSMB review): Males and females between 1 year to 18 years of age,

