10.3.3.2. Blood Loss

10.3.3.2.1. Blood Loss Calculation

Blood loss will be calculated using the following formula [15], [48]:

$$Blood\ Loss\ (mL) = \frac{RBCV_{before} + (Transfusion\ RBCV) - RBCV_{after}}{Hct_{after} [\%] * 0.01}$$

RBCV (mL) = Red Blood Cell Volume (mL) = Body Weight (kg) * 80 (mL/kg) * (Hematocrit [%] * 0.01)

Transfusion RBCV (mL) = [Total Volume (mL) of Whole Blood Transfused * 0.3] + [Total Volume (mL) of Packed Red Blood Cells Transfused * 0.8]

The blood loss will be computed over the whole eschar removal period, using the formula above, i.e. the eschar removal process will be considered as one continuous procedure. Therefore, only the Hematocrit value before the first eschar removal procedure and after the last procedure will be used and all blood transfusions performed between these measurements will be included.

Additionally, the blood loss will be summed over all procedures carried out to remove eschar, with the hematocrit measured immediately before each procedure and 4 hours after its completion. The amount of blood transfused will be summed over all transfusions carried out during the debridement procedure and up to 24 hours from the end time of the debridement procedure.

Analyses with both blood loss values will be conducted. However, some missing values are expected. The analysis with less missing values will be regarded as more reliable and is therefore considered the main analysis. The other analysis is considered supportive.

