11.1.6.6. Blood loss using changes in hemoglobin following eschar removal procedures

The measure of blood loss defined in Section 10.3.5.6 will be computed for each patient, presented by treatment group using descriptive statistics and compared between groups with a one-way analysis of variance.

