11.1.9. Handling of Multiple Comparisons

Unless otherwise specified, all statistical tests will be conducted against a two-sided alternative hypothesis, employing a significance level of 0.05. The primary and secondary endpoints of efficacy will be tested in a hierarchy, so as to preserve the nominal significance levels:

- 1. Primary: time to complete eschar removal
- 2. Secondary: Incidence of surgical excision
- 3. Secondary: Blood loss
- 4. Secondary: Area of Autograft in DPT wounds

5. Secondary: Incidence of Autograft in DPT wounds

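### The exploratory hemoglobin-based blood-loss measure has no transfusion term, so it understates loss in patients transfused before the later sample

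*SAP*

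**What the plan says.** SAP 7.2.4 lists as an exploratory analysis "Blood loss related to eschar removal assessed by changes in Hemoglobin incurred during the eschar removal procedures". SAP 10.3.5.6 derives it in two ways:

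- **Summed version.** For each procedure the change is "the difference of the hemoglobin value before the procedure and the hemoglobin value 4 hours post the procedure", and then "This difference in hemoglobin values will be summed for each patient".
- **First-to-last version.** This is "the difference of the hemoglobin value prior to the first debridement procedure and the hemoglobin value 4 hours post the last debridement procedure".

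Neither derivation mentions transfusion. SAP 11.1.6.6 treats the result as a measure of blood loss, "compared between groups with a one-way analysis of variance". It plans no transfusion covariate, exclusion, split or caveat.

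The secondary endpoint, which stands in the testing order of SAP 11.1.9 as "3. Secondary: Blood loss", handles the same construct differently. Its formula in SAP 10.3.3.2.1 adds a Transfusion RBCV term to the numerator: whole-blood volume times 0.3 plus "Total Volume (mL) of Packed Red Blood Cells Transfused * 0.8". When eschar removal is treated as one continuous procedure, "all blood transfusions performed between these measurements will be included". When loss is summed by procedure, transfusions during the procedure and in the 24 hours after it are counted.

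**The concern.** A pre-to-post change in hemoglobin reflects bleeding less whatever transfusion has put back. The SAP accepts this for hematocrit and gives no reason for treating hemoglobin otherwise.

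The sampling rules leave room for the problem. The first-to-last version spans the whole eschar-removal period, so any transfusion before the final sample raises the closing value. For the summed version, SAP 10.3.4.4 accepts central-laboratory post-procedure samples up to 24 hours after the procedure ends, so a nominal 4-hour sample can follow a transfusion.

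The planning data in SAP 9.1.3 and 13.3 show more blood loss under standard of care: 1024.27 against 421.93 mL in MW2004-11-02, and 814.51 against 14.17 mL in MW2010-03-02. If transfusion follows bleeding, more of the loss is hidden in that arm. The hemoglobin comparison could then appear weaker than the secondary result, or at odds with it, for reasons of measurement alone.

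**Working it through.** The plan states no effect size, power or sample size for the hemoglobin measure, so there is no figure of its own to reproduce. The check is a red-cell balance that compares the two definitions on the same bleed.

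**Inputs from SAP 10.3.3.2.1:** blood volume 80 mL/kg; packed cells x 0.8; blood loss = (RBCV before + Transfusion RBCV - RBCV after) / hematocrit after.

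**Assumptions for illustration only:** a 20 kg child; starting hematocrit 36%; hemoglobin per unit of red cells (MCHC) 333 g/L, that is, hemoglobin in g/dL is hematocrit in % divided by 3; constant blood volume.

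**One procedure, 400 mL lost.**

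- Blood volume = 20 x 80 = 1600 mL. RBCV before = 1600 x 0.36 = 576 mL.
- Red cells lost = 400 x 0.36 = 144 mL.
- The share replaced before the post sample is varied. With half replaced, 90 mL of packed cells gives 90 x 0.8 = 72 mL of red cells. RBCV after = 576 - 144 + 72 = 504 mL and hematocrit after = 504/1600 = 31.5%. The hemoglobin fall is (36 - 31.5)/3 = 1.5 g/dL = 15 g/L. The SAP formula gives (576 + 72 - 504)/0.315 = 457 mL.

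| Lost red cells replaced | Packed cells (mL) | Hematocrit after | Raw hemoglobin fall (g/L) | SAP hematocrit formula (mL) |
|---|---|---|---|---|
| 0% | 0 | 27.0% | 30 | 533 |
| 50% | 90 | 31.5% | 15 | 457 |
| 100% | 180 | 36.0% | 0 | 400 |
| 125% | 225 | 38.25% | -7.5 | 377 |

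The same bleed therefore reads as a large fall, half that fall, nothing, or a gain. The hematocrit formula also varies with replacement, but it always shows a substantial loss.

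**Timing: two procedures, 200 mL lost in each.**

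| Transfusion | Summed fall (g/L) | First-to-last fall (g/L) |
|---|---|---|
| None | 28.1 | 28.1 |
| Full replacement before each post sample | 0 | 0 |
| First loss fully replaced, between the first post sample and the second pre sample | 30 | 15 |

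In the last row, hematocrit goes from 36% to 31.5%, back to 36%, then to 31.5%. The summed version records both falls (15 + 15). The first-to-last version records only 36% to 31.5%. A transfusion after the last post sample alters neither version.

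**Can the transfusion be added back?** Transfusion RBCV is in mL of red cells, whereas SAP 13.2.2 lists hemoglobin in g/L, so the two cannot be added directly. The conversion is Transfusion RBCV x MCHC / (weight x 80). With full replacement it gives 144 x 333 / 1600 = 30 g/L. Raw fall plus correction is then:

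- 0%: 30 + 0 = 30 g/L
- 50%: 15 + 72 x 333/1600 = 15 + 15 = 30 g/L
- 100%: 0 + 30 = 30 g/L
- 125%: -7.5 + 180 x 333/1600 = -7.5 + 37.5 = 30 g/L

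The agreement follows from the illustration's assumptions. It confirms the units and the form of the correction, not its accuracy in real patients.

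**The case against.** The strongest reply is that little depends on this measure. It is exploratory, and the protocol synopsis itself names it as a change in hemoglobin, so a raw change implements what was promised. The blood-loss endpoint in the testing order already credits transfusions, under two methods. SAP 11.1.5.8 also reports transfusion volume by arm, including separately for the eschar-removal period, so a reader can see any imbalance. All of this stands, and it sets the weight of the point. It does not remove the point, because a table of volumes shows an imbalance without correcting the hemoglobin comparison.

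A reader might infer two stronger things that the documents do not support:

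- **That transfused patients appear to have lost no blood.** That needs full red-cell replacement before the post sample. Partial replacement only reduces the fall, and the summed version is not masked by a transfusion given between one post sample and a separate next pre sample. The 400 mL example is a quarter of the assumed 1600 mL blood volume, and nothing in the documents calls that typical.
- **That the arm comparison is known to be biased against NexoBrid.** The documents give no transfusion rates or volumes by arm. The planning means come from a study of adults and children (MW2004-11-02, SAP 9.1) and from an adult study (MW2010-03-02, SAP 13.3). SAP 13.3 says the latter used a different blood-loss formula.

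**Conclusion.** The omission is real and of minor consequence. As written, the exploratory hemoglobin measure understates blood loss in any patient transfused between the samples being compared, and the first-to-last version is the more exposed of the two. In the illustration, the understatement at half replacement is half of the 30 g/L fall.

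A pull toward no difference between arms rests on two assumptions: that transfusion follows bleeding, and that standard of care bleeds more in this trial. Both are plausible, but neither is shown for these children. The size of the effect cannot be computed from the documents and may be small. No sample size, significance level or confirmatory conclusion depends on it, and a discordant hemoglobin result should not by itself be read against the secondary blood-loss endpoint.

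**What to change.** In SAP 10.3.5.6 and 11.1.6.6:

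1. Keep the raw change, as the protocol names it, and label it as not corrected for transfusion.
2. Add a corrected version: hemoglobin fall + Transfusion RBCV x MCHC / (weight x 80 mL/kg), with hemoglobin and MCHC both in g/L and Transfusion RBCV as in SAP 10.3.3.2.1.
3. Count only transfusions given between the pre and post samples actually used: within each procedure's pair for the summed version, and between the first pre and last post sample for the first-to-last version. The 24-hour window of the per-procedure hematocrit method should not be borrowed, because it can credit a transfusion given after the post sample.
4. Report the number of patients transfused in each arm beside both versions.

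The cost is one extra derivation. Weight, transfusion volumes and MCHC are already collected (SAP 7.2.1, 10.3.4.4 and 7.2.3.5), and the per-procedure hematocrit method already requires transfusion timing. The correction assumes a blood volume of 80 mL/kg, as SAP 10.3.3.2.1 already does, and applies the patient's MCHC to donor cells. State which MCHC value is used.

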10.3.5.7. POSAS

The Patient Observer Scar Assessment Scale (POSAS) consists of two parts: a patient scale and an observer scale. Both scales contain six items that are scored numerically with 1-10. For each wound of a patient the total score of the patient scale will be computed as:

$$POSAS_P = \sum_{i=1}^{6} p_i,$$

where p_i is the score the patient assigned to item i. The total score of the observer scale will be computed analogously as:

$$POSAS_O = \sum_{i=1}^6 o_i,$$

where o_i is the score the observer assigned to item i.

A total score for the POSAS is then obtained by summing the patient scale score and the observer scale score:

$$POSAS_{tot} = POSAS_P + POSAS_O$$
.

For each patient the mean over all TWs will be computed separately for $POSAS_{tot}$, $POSAS_{P}$ and $POSAS_{Q}$.

The POSAS will be computed for TWs at the long-term follow up visits.

10.3.5.8. Duration of hospitalization

Duration of acute hospitalization will be computed as the difference in days between hospital admission and hospital discharge (initial hospitalization only). Subjects without a discharge date will be censored at the date of death (if applicable) or date of last known assessment performed during initial hospitalization period.

10.3.6. Laboratory Values

The following transformations will be applied to the central laboratory data obtained pre and post the eschar removal procedures:

Laboratory findings that are given in various units will be transformed to standard units. Laboratory values will be categorized as "abnormal (low)", "normal" and "abnormal (high)" based on the reference limits of the labs.

Pre-post differences of laboratory values for each eschar removal procedure will be calculated (difference between post-procedure value and pre-procedure value).

Absolute and relative frequencies of "abnormal (low)", "normal" and "abnormal (high)" findings will be calculated per laboratory value, eschar removal procedure and treatment arm.

10.4. Multiple Visits Per Time Point

Study visit time-points are scheduled at screening, pre eschar removal, eschar removal (treatment), post-treatment, hospital discharge, follow-up (weekly until wound closure, wound closure confirmation), long-term follow-up at 6 and 12 weeks and at 6, 12, 18 months and 24 months post wound closure confirmation and re-admission to hospital/day care (if done). One visit is expected for each time-point.

For all endpoints, if a subject has more than one visit with data at a time-point, the later non-missing evaluation will be used for analyses.

10.5. Implications of COVID-19 Pandemic to the Study Data

This section describes how deviations related to COVID-19 pandemic will be handled.

10.5.1. Handling of Missing Values

Data missing due to COVID-19 will be handled in the same way as missing data for any other reason, i.e. the procedures for handling of missing data described in the SAP in Section 10.1 will also be applied to missing values due to COVID-19.

10.5.2. Handling of Remotely Captured Data

Due to COVID-19 restrictions, the sponsor has submitted a protocol memo (see SAP Section 13.4), dated 09 Apr 2020, to sites allowing them to perform long-term follow-up visits

remotely. All visits could have been performed remotely, but at the time of COVID-19 outbreak almost all patients had already been post 12 weeks FU visit, so it is expected a large portion of remote assessments starting from the 6 months FU visit and onwards.

Apart from MVSS and POSAS assessments, all endpoints, allowed to be evaluated remotely during long-term follow-up visits, are self-reported. Therefore, no influence of remote study visits is expected. For MVSS and POSAS assessments, the possible influence of remotely captured data will be addressed as described in the following sub-sections.

10.5.2.1. Cosmesis and Function at 12 Months from Wound Closure

For the purpose of the main analysis, all values (both on-site and remotely collected) will be used, with missing values imputed as described in SAP Section 10.1.4.2.

For the purpose of the sensitivity analysis, to explore the possible influence of remotely captured data, the following procedure will be applied:

- 1. For a time point t=12 months take a subset of subjects in each treatment group who have *on-site* evaluations X_{12m} or *remote* evaluations Y_{12m} (at least 10 subjects with *on-site* evaluations at 12 months, and at least 10 subjects with *remote* evaluations at 12 months in each treatment group), and also have *on-site* evaluations for all previous time points (6 weeks, 12 weeks and 6 months). In case such a subset cannot be obtained due to absence of sufficient *on-site* values at time point 6 months, a subset with *on-site* evaluations for time points 6 weeks and 12 weeks will be considered. Denote the set of relevant previous time points as (t-1,...,1).
- 2. Separately for each treatment group, regress Y_{12m} on $x_{t-1} = (1, X_{t-1}, ..., X_1)$ and all stratification variables (S) (see Section 11.1.11), where Y_{12m} are the *remote* evaluations at 12 months (from a subset of subjects obtained at the first step), x_{t-1} are the *on-site* evaluations at previous times (for subjects with Y_{12m}) and "1" is to indicate regression with intercept. For each regression:
 - a. Obtain the estimate of residual variance, denote by $\widehat{\sigma_R^2}$.
 - b. Obtain a prediction formula $\widehat{Y_{12m}} = H(x_{t-1}, S)$ to predict Y_{12m} given x_{t-1} and S.
 - c. Apply this formula to the (x_{t-1},S) of the subjects who had on-site evaluations X_{12m} (from a subset of subjects obtained at the first step). For each such subject there will be both X_{12m} and $\widehat{Y_{12m}}$.

- d. Estimate the mean Bias $\widehat{\mu_B}$ using the mean of the differences $D_{12m} = X_{12m} \widehat{Y_{12m}}$ for those subjects.
- e. Estimate the variance of the Bias $\widehat{\sigma_B^2}$ by the estimate of the variance $(\widehat{\sigma_D^2})$ of the differences $D_{12m} = X_{12m} \widehat{Y_{12m}}$ plus $\widehat{\sigma_R^2}$. That is $\widehat{\sigma_B^2} = \widehat{\sigma_D^2} + \widehat{\sigma_R^2}$.
- 3. For the sensitivity analysis of MVSS at 12 months:
 - a. Take the *remote* evaluations Y_{12m} and add to each a random normal variate with mean $\widehat{\mu_B}$ and variance $\widehat{\sigma_B^2}$ (for the appropriate treatment group). This will provide a "correction" to *remote* evaluations, as if they were observed during an on-site visit.
 - b. Repeat step a for each previous time point separately to get the "corrected" remote evaluations. All these "corrections" (biases) would be sampled from the same fixed distribution with mean $\widehat{\mu_B}$ and variance $\widehat{\sigma_B^2}$, estimated at step 2 above.
 - c. Impute missing MVSS values at 12 months, applying the imputation procedure from SAP Section 10.1.4.2 on observed *on-site* evaluations and "corrected" *remote* evaluations.

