10.5.2.2. Cosmesis and Function at 24 Months from Wound Closure

For the purpose of the main analysis, all values (both on-site and remotely collected) will be used, with missing values imputed as described in SAP Section 10.1.4.2.

For the purpose of the sensitivity analysis, to explore the possible influence of remotely captured data, the following procedure will be applied:

- 1. Repeat step 3a from the above section (10.5.2.1) for additional follow-up time points 18 months and 24 months, to get the "corrected" *remote* evaluations.
- 2. Impute missing MVSS values at 24 months, applying the imputation procedure from SAP Section 10.1.4.2 on observed on-site evaluations and "corrected" remote evaluations from all previous time points (for time points up to 12 months previously "corrected" remote evaluations can be used).

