Difference: -1.38; Standard error of difference: 0.44

Anticipated difference: -1.38 + 0.44 / 2 = -1.16

The non-inferiority margin employed for this analysis is 1.9 score points.

Using a one-sided two-sample t-test with a significance level of 2.5%, 36 evaluable subjects are needed (18 in each group) to achieve a power of 90%. Using a conservative rate of missing values of 30%, the total sample sizes needed to achieve a power of 90% in the analysis is 52 (26 per group).

Note: In the analysis missing data will be imputed, leading to more evaluable subjects, increasing the power.

Cosmesis and Function: MVSS at 24 months

Estimate based on study MW2004-11-02

Estimated difference in MVSS at 24 months from previous study (NexoBrid vs. SoC) = 3.32 - 3.83 = -0.51.

Standard error = 0.50

Target difference $\Delta = -0.51 + 0.50/2 = -0.26$.

The formula for the number of patients per group n is: $n = \frac{2(z_{\alpha} + z_{\beta})^2 \sigma^2}{q(\Delta - d_0)^2}$

where

 $z_{\alpha} = 1.96$;

 z_{β} = 1.28 for a power of 0.9;

 σ = the estimated common standard deviation= 2.33 (taken from previous study);

 d_0 = clinical equivalence level = 1.9;

q = proportion who are retained in follow-up to 24 months = 0.5 (assuming 50% loss to follow-up over 2 years)

For 90% overall power, the required sample size per group is 49 (98 overall).

Estimate based on study MW2010-03-02

Since at this time the 24 months MVSS data of the MW2010-03-02 study is not yet available, the 12 months data will be used for the calculation.

Estimated mean MVSS at 12 months from study MW2010-03-02: NexoBrid 3.70; SoC 5.08

Standard errors: NexoBrid 0.24; SoC 0.38

Difference: -1.38; Standard error of difference: 0.44

Anticipated difference: -1.38 + 0.44 / 2 = -1.16

The non-inferiority margin employed for this analysis is 1.9 score points.

Using a one-sided two-sample t-test with a significance level of 2.5%, 36 evaluable subjects are needed (18 in each group) to achieve a power of 90%. Using a conservative rate of missing values of 50%, the total sample sizes needed to achieve a power of 90% in the analysis is 72 (36 per group).

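### The sensitivity analysis for remotely scored MVSS treats an estimated, arm-specific bias as known, so the interval it compares with 1.9 is too narrow

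*SAP*

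**What the plan says.** SAP 10.5.2 expects remote follow-up to be common: "it is expected a large portion of remote assessments starting from the 6 months FU visit and onwards". The main MVSS analysis uses on-site and remote scores as recorded. SAP 10.5.2.1 adds a sensitivity analysis, which works as follows in each arm.

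- **Step 1** takes a subset with on-site scores at the earlier visits. It asks for "at least 10 subjects with *on-site* evaluations at 12 months, and at least 10 subjects with *remote* evaluations" at 12 months in each arm.
- **Step 2** regresses the remote 12-month scores on the earlier on-site scores and "all stratification variables (S) (see Section 11.1.11", and predicts a remote score for each on-site patient. The mean of on-site minus predicted score is the estimated bias. Step 2e, "Estimate the variance of the Bias", adds the variance of those differences (sigma_D^2) to the residual variance of the regression (sigma_R^2).
- **Step 3** is to take the remote scores and "add to each a random normal variate with mean" and variance equal to those step 2 estimates, one draw per score. Corrections at earlier visits "would be sampled from the same fixed distribution with mean" and variance fixed in step 2.

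SAP 10.5.2.2 extends this: "Repeat step 3a from the above section (10.5.2.1) for additional follow-up time points 18 months and 24 months". SAP 11.1.5.2 and 11.2.4.3 then fit the planned linear model to the corrected scores and declare non-inferiority if the upper 95% limit is below 1.9.

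**The concern.** The bias is an estimate, possibly from very few patients, but it enters the analysis as a constant. After the shift, the mean of an arm's remote patients is essentially a prediction from its on-site patients. The linear model nevertheless counts the remote patients as independent information, so it reports too small a standard error.

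The added noise is a second matter. A remote score already has its own residual variance, and an independent draw is placed on top of it. Even if on-site and remote residuals for one scar were unrelated, their difference would be negatively correlated with the remote score. An independent draw therefore cannot turn a remote score into an on-site one.

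What is at stake is the only planned check of remote scoring for the 12- and 24-month MVSS tests against 1.9. A check with too narrow an interval can reassure when it should not.

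**Working it through.** **The plan's own figure.** SAP 13.3 states: "The non-inferiority margin employed for this analysis is 1.9 score points". With its first-study inputs (SD 2.33, anticipated difference -0.26, z-values 1.96 and 1.28), evaluable patients per arm = 2 × 3.24² × 2.33² / (-0.26 - 1.9)² = 24.43. Dividing by 0.7 retained gives 34.9, so 35 per group at 12 months. Dividing by 0.5 gives 48.9, so 49 at 24 months. Both match the SAP.

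**Inputs for the check.** 145 patients randomized 1:1, so about 72 per arm; SD 2.33; margin 1.9; one-sided 2.5%. The documents give neither the remote share f nor the between-visit correlation. I assume f from 20% to 70% and correlations from 0.3 to 0.8.

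**Closed form, no covariates, same f in both arms.** The estimated bias is the on-site mean minus the remote mean. The arm mean after correction is therefore the on-site mean plus f times the average noise. Here sigma_D^2 = sigma_R^2 = σ², so the noise has variance 2σ² and a corrected score has variance 3σ².

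- True variance of the arm mean: (σ²/n) × [1/(1-f) + 2f]
- Variance the model reports: (σ²/n) × [(1-f) + 3f] = (σ²/n) × (1 + 2f)

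At f = 0.5 the ratio of true to reported SE is √(3/2) = 1.225. The error rate is 1 - Φ(1.96/1.225) = 5.5%. Across f:

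| Remote share | 20% | 30% | 40% | 50% | 60% | 70% |
|---|---|---|---|---|---|---|
| False non-inferiority | 3.6% | 4.1% | 4.7% | 5.5% | 6.5% | 8.1% |

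Without the noise, the true and reported variances are proportional to 1/(1-f) and 1. At f = 0.5 the error rate would be 1 - Φ(1.96/1.414) = 8.3%. The noise therefore lowers the error rate, while raising the reported SE by √2, or 41%.

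**Simulation of steps 1 to 3a at a true difference of 1.9** (2,000 to 3,000 runs per row, no missing data, correlation 0.6 and region included unless stated):

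| Setting | Uncorrected | As planned | Shift only, no noise | Bias redrawn, 25 sets | True SD / reported SE, as planned |
|---|---|---|---|---|---|
| 30% remote | 2.5% | 4.7% | 6.0% | 2.1% | 1.16 |
| 40% remote | 2.6% | 4.8% | 7.1% | 2.1% | 1.21 |
| 50% remote | 2.1% | 5.2% | 7.3% | 1.6% | 1.22 |
| 70% remote | 2.0% | 7.7% | 11.1% | 1.5% | 1.37 |
| 50%, correlation 0.3 | 2.0% | 6.1% | 9.4% | 2.1% | 1.26 |
| 50%, correlation 0.8 | 2.9% | 4.3% | 4.9% | 2.5% | 1.16 |
| 50%, of whom 40% also remote at 6 months | 2.5% | 8.1% | 12.3% | 2.1% | 1.40 |
| 25%, no region | 2.4% | 3.3% | 4.0% | 2.3% | 1.13 |
| 70%, of whom half also remote at 6 months, no region | 3.1% | 10.1% | 16.3% | 1.7% | 1.58 |

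The planned procedure runs from 3.3/2.5 = 1.3 to 10.1/2.5 = 4.0 times nominal. Monte Carlo error on a 5% rate with 3,000 runs is √(0.05 × 0.95/3,000) = 0.4 percentage points.

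**Parameters in the step 2 regression.** Intercept 1, earlier MVSS scores 3, age group 3, %TBSA 1, full-thickness share 1, and center 3 if grouped into the four regions of SAP 11.1.8. The total is 12. The fallback to two earlier visits gives 11. SAP 11.1.11 lists individual centers, which would add more. With 10 remote patients there are no residual degrees of freedom, and sigma_R^2 cannot be estimated.

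**The case against.** The strongest reply is that little depends on this analysis. SAP 11.1.5.2 calls it exploratory of the influence of remote data, the main analysis uses uncorrected scores, MVSS is outside the hierarchy in SAP 11.1.9, and SAP 11.2.8 declares all second-stage testing exploratory. Other analyses also look at remote scar scoring: SAP 11.1.6.7, 11.1.6.8, 11.2.5.1 and 11.2.5.2 repeat POSAS up to 24 months, and MVSS at 6 and 12 weeks, 6 months and 18 months, without remote data. This stands and limits the weight of the point. It does not remove it, because none of those repeats covers MVSS at 12 or 24 months.

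A second reply is that the procedure rightly lets the bias differ between arms, and that the added noise makes it cautious. The first half stands, and any replacement must keep it. The second half does not: the noise widens the reported interval, but not by enough.

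A reader might also infer a serious loss of power. At a true difference of 0.5, success falls from about 95% to about 73% with half the scores remote. But 0.5 is not a planning value in the documents, and a valid model with arm-specific remote bias also gives about 73% there. At the SAP's own -0.26 with 50% remote, success is still 95% to 97%.

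**Conclusion.** The point holds for the sensitivity analysis only. Its reported standard error is too small (true SD 1.13 to 1.58 times the mean reported SE), and its false non-inferiority rate is about 1.3 to 4 times 2.5%. About twice nominal applies if 30% to 50% of 12-month scores are remote and earlier visits were on-site. The direction follows from the written procedure; the multiple depends on the assumed remote share, between-visit correlation and earlier remote visits. The calculations leave out the single imputation of missing scores in SAP 10.1.4.2, which is a separate matter.

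Three stronger readings are tempting but unsupported. The added variance does not cause the inflation: without it the error rate is higher. A doubled error rate is not a fact about this trial, since the documents give no remote share. And the main MVSS conclusion is not undermined, because it does not use the corrected scores.

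**What to change.** For this sensitivity analysis at 12 and 24 months, replace steps 2 and 3 of SAP 10.5.2.1 and the matching text of 10.5.2.2. Any one of these would do:

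1. **Preferred.** Set remote MVSS scores to missing and impute them 25 times per arm from the on-site regression, drawing the regression parameters each time. Fit the planned model to each data set and pool by Rubin's rules. In simulation this held 2.3% to 2.9%. The SAP already uses 25 imputations with pooling for blood loss and autograft area (10.1.3.2 and 10.1.3.3).
2. Keep the shift, but draw each arm's mean bias from its sampling distribution in 25 data sets, without patient-level noise, and pool. This held 1.5% to 2.5%. Success at -0.26 with 50% remote was 96%, against 95% as planned.
3. Add remote and remote-by-treatment terms to the planned model and report the on-site treatment effect.

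A common remote indicator alone should not be used, because it assumes the same bias in both arms. If remote scoring favored NexoBrid by 1 point with 50% remote, false non-inferiority would be 23% to 26%, against about 5% to 6% for the present procedure.

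Whichever regression remains, shorten its covariate list or raise the minimum number of patients well above its parameter count, and state whether center means site or region.

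The cost is SAP wording and code; no new data are needed. The interval will be wider than in the uncorrected main analysis, and option 1 does not use the remote scores. Option 1 also assumes that, given earlier scores and strata, remote and on-site patients would have had similar on-site scores. The present correction needs the same assumption.
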